#### 8.1.3 Relative Day

For listings that include visit/event dates, the relative day will also be listed. The relative day will be expressed using the following methodology:

- Date of first dose of study drug is Relative Day 1.
- No Day 0 will be used.
- For visit/event dates that occurred before the date of the first dose of study drug, the Relative Day will be expressed with a minus (-) sign followed by the number of days before the date of first dose of study drug that correspond to the date of the visit/event.
- For visit/event dates that occurred after the date of the last dose of study drug, the Relative Day will be expressed with a plus (+) sign followed by the number of days after the date of the last dose of study drug that correspond to the date of the visit/event.
- Relative Days shown without a minus or plus sign will correspond to the day to dosing.

Assessment windowing, as described in Sections 8.1.1 and 8.1.2, will be performed using the Relative Day.

#### 8.2 Adjustments for Interim Analyses and Multiplicity of Endpoints

The study has a single primary effectiveness endpoint and there are no planned interim analyses; hence, no adjustment for multiplicity will be implemented.

Form STAT401.V3 Page 10 of 23

Client/Project	Arrivo/Sirtsei 201
Version and Date	V01 August 26, 2022

#### 8.3 Evaluations and Statistical Analyses

#### 8.3.1 Subject Disposition

Subject disposition will include total number of subjects summarized by number screened and number of screen failures if they are recorded in the database. Summaries will include the number of subjects randomized by treatment group and overall. Summaries for randomized subjects who completed the study treatment period and as well as those who withdrew from the study treatment period will be summarized by number of subjects and percentages of subjects. Summaries for randomized subject who completed the follow up period and as well as those who withdrew from the follow up period will be summarized by number of subjects and percentages of subjects. Finally, the reasons for withdrawing from the study treatment period and follow up period will be summarized. Totals and percentages of subjects in each analysis dataset will be tabulated by treatment arm.

#### 8.3.2 Protocol Deviations

Protocol deviations will be divided into minor protocol deviations and major protocol deviations, per Investigator and summarized using the safety population. For each protocol deviation type and study event, the count and percentage of subjects with that protocol deviation will be summarized by treatment group and overall. The total number of protocol deviations of that type will also be presented by treatment group and overall.

Protocol deviations will be listed using the all subjects population.

#### **8.3.3** Demographics and Baseline Characteristics

Demographics information will be summarized using descriptive statistics. For gender, race, and ethnicity the summarization of those categorical values will be performed using percentages and frequency. Age (at Screen), height, weight (at Screen and Baseline), and BMI (at Screen and Baseline) will be summarized using descriptive statistics as total number of subjects surveyed (N), mean, median, minimum, and maximum.

Listings and summaries of demographics, body measurements at Screen and Baseline, medical history, depression and current depressive episode history, and current depressive episode treatment history will be provided for the mITT or safety populations.

#### 8.3.3.1 Concomitant Medications

Concomitant medications will be tabulated by major therapeutic class and coded medication name, but no formal analyses will be performed. Number and percentage of subjects will be presented by treatment group and overall. Concomitant medication summaries will be presented separately for the following:

- Concomitant Medications taken during the Treatment Period (ie, either taken or continuing from date of first dose of study drug to date of last dose of study drug for each subject); and
- Concomitant Medications taken during the Follow-up Period (ie, either taken or continuing after date of last dose of study drug for each subject).

Medications taken and stopped prior to first dose of study drug (ie, prior medications) will be included in the listing, but will not be summarized as a concomitant medication.

#### 8.3.4 Treatment Administration and Compliance

Descriptive numerical summaries (N, mean, standard deviation, median, minimum, and maximum) will be presented for both the total drug exposure in days and total drug exposure in number of capsules per day by treatment group and overall. The percent compliant with prescribed dosing during the treatment period will similarly be summarized descriptively. Counts and percentages of subjects that met total days of study drug exposure marks as well as overall total days of study drug exposure will be summarized

Form STAT401.V3 Page 11 of 23

Client/Project	Arrivo/Sirtsei 201
Version and Date	V01 August 26, 2022

categorically by study week. Counts and percentages will also be shown for number of subjects by total percent compliance with prescribed dosing during the treatment period and number of subjects for whom the prescribed dose was reduced from two capsules a day to one capsule a day.

#### 8.3.5 Primary Estimand

The primary efficacy estimand, is comprised of the primary endpoint, target population, intercurrent events of interest and strategy for addressing them, analysis approach to compare treatments and summary measure (hypothesis to be tested).

#### 8.3.5.1 Primary Efficacy Endpoint

The primary efficacy endpoint for this study is the change from Baseline to Week 4 in total MADRS score. Efficacy analyses will be conducted using the mITT population, assuming subjects had dosed as directed for 4 weeks.

#### 8.3.5.2 Intercurrent Events of Interest and Strategy for Addressing

The intercurrent events of interest and strategy for addressing is given in the following table:

**Table 8.1, Handling of Intercurrent Events** 

Estimand	Intercurrent Event	Rule / Rationale
Primary	Premature discontinuation /	Hypothetical "as own treatment" strategy. Clinical
	Permanent treatment	course is the same as other subjects in the same
	discontinuation	treatment group, who had not discontinued study
		treatment.
		Exclude observations that occur more than 3 days
		after the last dose of study drug for subjects who
		discontinue. The objective of the study is to
		evaluate the effect of SP-624 subjects who are
		provided drug to take on a standard schedule up to 4
		weeks. After 3 days, the drug should be cleared
		from all subjects, so the inclusion of any such data
		point is inconsistent with the goal of the estimand.
	Drug non-compliance / Missed	Treatment policy strategy.
	study medication	Some degree of non-compliance missed doses
		would be expected to occur in standard use.
	Protocol deviations not leading	Treatment policy strategy
	to study discontinuation	Overall, if not sufficient to lead to subject removal,
		the expectation is that they would not significantly
		impact subject results.
	Concomitant medications in	Treatment policy strategy
	violation of the protocol	This is expected to be a rare event in this clinical
		trial and treatment effect will be estimated
		irrespective of concomitant medication violations.

The hypothetical "as own treatment" strategy was selected for premature discontinuation or treatment discontinuation intercurrent events to evaluate the effect of treatment with respect to its pharmacologic efficacy. For the change from week 4 to week 5 follow-up secondary analysis, only subjects that were included in the week 4 primary analysis will be used. This should provide the most unbiased data for this

Form STAT401.V3 Page 12 of 23

Client/Project	Arrivo/Sirtsei 201
Version and Date	V01 August 26, 2022

phase 2 study to inform future studies. The treatment policy strategy will be used for all other defined intercurrent events.

#### 8.3.5.3 Primary Efficacy Hypothesis

The null hypothesis is that the mean change from Baseline to Week 4 in total MADRS score will be the same in both groups. The following hypothesis statement to be tested for the comparison of the primary efficacy endpoint is:

$$H_0$$
:  $\mu_{SP-624} = \mu_{Control}$  versus  $H_1$ :  $\mu_{SP-624} > \mu_{Control}$ 

Where  $\mu_{SP-624}$  is the mean change in MADRS score from baseline to week 4 for the SP-624 group and  $\mu_{Control}$  is the mean change for the control group.

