9.3. Description of Statistical Methods

9.3.1. General Approach

All data will be provided in listing files. Study results and information will be displayed in descriptive summary tables. Inferential tests are identified below. For measurements that have multiple intermediate visits, results for observed data will be summarized for each time.

When comparisons between groups are performed, two-sided tests at a 0.05 level of significance ($\alpha=0.05$) will be used. The null hypothesis for all analyses is that there is no difference between the SP-624 and placebo treatment groups. There is only one primary outcome for analysis, and there will be no adjustment for multiplicity for secondary endpoints.

All summaries, statistical analyses, and individual subject data listings described below will be completed using Version 9.4 or later of the SAS Statistical Analysis System (SAS Institute, Inc. Cary, NC).

Subjects who are randomized but not treated and those who are treated but have no post-treatment follow-up assessments or data will be listed, but not analyzed.

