#### 8 Statistical Methods

#### 8.1 General Reporting Conventions

Study data will be provided in listings and sorted by subject number, study period, and assessment time. The study results will be displayed using descriptive summary tables and inferential analyses completed as described below. Summaries will be displayed by group for all tables and, optionally, for all subjects for baseline tables. For measurements that have multiple intermediate visits, results for observed data will be summarized for each time.

Standard numeric descriptive statistics include number of subjects or records observed (N), mean, standard deviation (std), median, minimum (min), and maximum (max) values. Standard categorical descriptive statistics include the count and percentages of subjects with a level of the variable summarized. Hypothesis tests will assess the null hypothesis that there is no difference in the treatment arms. Two-sided p-values of less than or equal to 0.05 will be considered statistically significant.

All summaries, statistical analyses, and individual subject data listings described below will be completed using Version 9.4 or later of the SAS Statistical Analysis System (SAS Institute, Inc. Cary, NC).

Subjects who are randomized but not treated and those who are treated but have no post-treatment follow-up assessments or data will be listed, but not analyzed. For all listings with dates, the relative study day will be presented, and a minus sign will denote study day is prior to first dose (day 1) while a plus sign will denote number of study days after last dose. Days occurring during treatment period will use neither a plus nor a minus sign.

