#### 8.3.5.4 Primary Efficacy Analysis

The primary efficacy hypothesis will be evaluated by comparing SP-624 to placebo using the mean change from baseline in total MADRS total score after 4 weeks of treatment using a Mixed Model for Repeated Measures (MMRM). The analysis model will include fixed effects for treatment, week and the interaction of week by treatment, and a random effect of subject within treatment. Baseline MADRS total score will be included as a covariate in the model. The treatment difference in terms of the mean change from baseline to a given time point will be estimated and tested from this model. An unstructured covariance matrix will be used to model the correlation among repeated measures. The Kenward-Rogers approximation will be used for the denominator degrees of freedom. The criterion for declaring SP-624 superior to placebo for MADRS total score change from baseline is that the p-value is less than or equal to 0.05.

In the event of a model which fails to converge, the following covariance structures will be considered (in order) until convergence is obtained:

- 1. Heterogenous Toeplitz
- 2. Toeplitz
- 3. First order auto-regressive [AR(1)]
- 4. Compound symmetry

If a covariance structure other than Type=UN is used, a sandwich estimator using the EMPIRICAL option on the PROC MIXED statement will be used.

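### The primary alternative hypothesis in SAP 8.3.5.3 is printed one-sided and in the direction of harm, against the plan's own two-sided 0.05 rule

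*SAP*

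**What the plan says.** SAP 8.3.5.3 states the null in words, that the "mean change from Baseline to Week 4 in total MADRS score will be the same in both groups", and sets against it the alternative "\mu_{SP-624} > \mu_{Control". It defines the first symbol thus: it "is the mean change in MADRS score from baseline to week 4 for the SP-624 group". The control symbol is defined in the same way.

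The general rules are two-sided. SAP 8.1 says "Two-sided p-values of less than or equal to 0.05 will be considered statistically significant" and "Hypothesis tests will assess the null hypothesis that there is no difference in the treatment arms". Protocol 9.3.1 calls for "two-sided tests at a 0.05 level of significance" when groups are compared, and adds: "The null hypothesis for all analyses is that there is no difference between the SP-624 and placebo treatment groups".

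The decision rule in SAP 8.3.5.4, for when the drug may be called better, reads in part: "superior to placebo for MADRS total score change from baseline is that the p-value is less than or equal to 0.05". It repeats neither the sidedness nor the direction. SAP 2.2, which lists changes to the planned analyses, mentions only the safety population, so no move to a one-sided test is declared.

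**The concern.** There are two separate faults in one line.

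- **Direction.** Improvement on MADRS is a fall in score, so benefit means a more negative mean change on SP-624. The printed alternative asserts the opposite.
- **Sidedness.** A one-sided alternative does not match the two-sided rule in SAP 8.1 and protocol 9.3.1, whichever way the sign is read.

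This line is the formal statement of the trial's only primary test, and the decision rule that follows it in 8.3.5.4 does not repair it. A programmer or reader who stays within 8.3.5 never meets the word two-sided and never sees a requirement that the difference favour SP-624. The likely wrong repair is to reverse the sign, leave the alternative one-sided and apply 0.05 to it. That would double the false-positive rate in the favourable direction.

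**Working it through.** **Inputs.** Expected decreases of 12 (SP-624) and 9 (placebo), SD 9.2 in both arms, difference 3, power 80%, 150 per arm (protocol 9.1; SAP 5). Allocation 1:1 (SAP 4). Dropout of 20-30% described as typical (protocol 9.3.5; SAP 8.3.5.5). Two-sided 0.05 (SAP 8.1; protocol 9.3.1).

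**1. Which test does the stated sample size fit?** The normal approximation is n per arm = 2(z_alpha + z_power)² × (SD/difference)².

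- Two-sided 0.05, or its equivalent one-sided 0.025: 2 × (1.960 + 0.842)² × (9.2/3)² = 147.6. The exact t calculation gives 149, with power 0.801.
- One-sided 0.05: 2 × (1.645 + 0.842)² × (9.2/3)² = 116.3. The exact t calculation gives 117, with power 0.800.

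The plan states 150, where the exact t power is 80.4% at two-sided 0.05 and 87.9% at one-sided 0.05. The sample size section names no sidedness, but its figure reproduces only under two-sided 0.05 or one-sided 0.025.

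**2. Direction.** The expected difference in mean change, SP-624 minus placebo, is -12 - (-9) = -3. The SAP uses the same sign for CGI-S in 8.3.6, another scale on which higher is worse: a change of -6 is improvement. With 150 per arm, SE = 9.2 × √(2/150) = 1.062, so an observed -3 gives t = -3/1.062 = -2.824 on 298 df.

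- Two-sided p = 0.0051.
- p in the tail named by the printed alternative = 0.9975.
- Power of the printed alternative at one-sided 0.05, if the true difference is -3: about 0.000004.

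Taken literally, the printed hypothesis could not detect the planned benefit.

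**3. Sidedness under the other reading.** If mu meant the size of the decrease, 12 > 9 would be the right direction. The alternative would still be one-sided, so the mismatch with SAP 8.1 and protocol 9.3.1 remains.

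**4. Cost of the likely wrong repair.** Suppose the sign is reversed, the one-sided form is kept and 0.05 is applied. The smallest significant benefit is the t critical value times the SE. Dropout of 20% leaves 150 × 0.8 = 120 per arm, and 30% leaves 150 × 0.7 = 105. The last column is the difference between the two powers at a true benefit of 3.

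| Observed per arm | SE | Critical benefit, two-sided 0.05 | Critical benefit, one-sided 0.05 | Power, two-sided | Power, one-sided | Chance the verdicts differ |
|---|---|---|---|---|---|---|
| 150 | 1.062 | 2.09 | 1.75 | 0.804 | 0.880 | 7.6% |
| 120 | 1.188 | 2.34 | 1.96 | 0.711 | 0.809 | 9.8% |
| 105 | 1.270 | 2.50 | 2.10 | 0.652 | 0.761 | 10.9% |

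With no true effect, the chance that the verdicts differ is 0.05 - 0.025 = 2.5% in every row.

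**The case against.** The strongest reply has four parts.

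- **Both faults rest on one symbol.** It was read by machine from a PDF whose text is visibly damaged elsewhere. A misread not-equal sign would remove both faults, and a null of equality pairs naturally with a not-equal alternative. This stands as a caution: check the page. It is not evidence of a misread, since the equals sign and the Greek letters in the same formula came through.
- **The operative rule is settled elsewhere.** SAP 8.1 applies to all hypothesis tests and supplies the sidedness that 8.3.5.4 omits, and the sample size agrees. This stands, and it is why the consequence is limited. It does not make the hypothesis line correct.
- **The sidedness point is mostly form.** A directional claim judged by a two-sided p-value at 0.05 has the same favourable rejection region as a one-sided test at 0.025. That is true once the direction is right, but neither 8.3.5.3 nor 8.3.5.4 says so.
- **The notation may simply be loose.** The sample size section gives unsigned decreases, in which 12 exceeds 9, and the negative-is-improvement rule is written out only for CGI-S. That is a plausible origin of the slip, but the SAP defines mu as mean change and not as reduction.

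It is also fair that the figures in the last step of the working measure one particular misreading and not the plan read as a whole.

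**Conclusion.** The concern holds. As printed, the primary alternative points towards harm and is one-sided, in conflict with the planned effect, SAP 8.1 and protocol 9.3.1. It is a specification error in a single line: the rest of the plan identifies a two-sided 0.05 superiority test, and 150 per arm was evidently sized for that or its one-sided 0.025 equivalent.

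The exposure is confined to a partial repair at one-sided 0.05. A two-sided p between 0.05 and 0.10 in favour of SP-624 would then be called superior. That would happen with probability 2.5% under no effect, and 7.6% to 10.9% at the planned effect depending on dropout.

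These figures assume equal arms, SD 9.2 and an unadjusted standard error. The rows for 120 and 105 count Week 4 completers only, so the MMRM standard error will differ because of baseline adjustment and data from earlier visits. The finding also assumes that the printed inequality sign is what the SAP page shows.

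**What to change.** Check the symbol on the SAP page, then make these changes.

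- **8.3.5.3:** state H0: mu(SP-624) = mu(Control) against H1: mu(SP-624) ≠ mu(Control), two-sided alpha 0.05, and note that a negative change is improvement.
- **8.3.5.4:** state that superiority requires a two-sided p-value of at most 0.05 and a Week 4 least-squares mean difference, SP-624 minus placebo, below zero.
- **8.3.5.5 (optional):** use that same criterion to define a positive primary analysis, since the tipping-point and multiple-imputation analyses depend on it.

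The cost is two lines of wording, or three with the option. Sample size, alpha, model and data collection do not change. The documents do not give the blinding status: the SAP is version 01 of 26 August 2022, and the protocol estimated the last visit for November 2021. If the data are still blinded, document the correction before unblinding. If not, record it as a dated correction that cites the two-sided rule already in SAP 8.1 and protocol 9.3.1.

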#### 8.3.5.4 Primary Efficacy Analysis

The primary efficacy hypothesis will be evaluated by comparing SP-624 to placebo using the mean change from baseline in total MADRS total score after 4 weeks of treatment using a Mixed Model for Repeated Measures (MMRM). The analysis model will include fixed effects for treatment, week and the interaction of week by treatment, and a random effect of subject within treatment. Baseline MADRS total score will be included as a covariate in the model. The treatment difference in terms of the mean change from baseline to a given time point will be estimated and tested from this model. An unstructured covariance matrix will be used to model the correlation among repeated measures. The Kenward-Rogers approximation will be used for the denominator degrees of freedom. The criterion for declaring SP-624 superior to placebo for MADRS total score change from baseline is that the p-value is less than or equal to 0.05.

In the event of a model which fails to converge, the following covariance structures will be considered (in order) until convergence is obtained:

- 1. Heterogenous Toeplitz
- 2. Toeplitz
- 3. First order auto-regressive [AR(1)]
- 4. Compound symmetry

If a covariance structure other than Type=UN is used, a sandwich estimator using the EMPIRICAL option on the PROC MIXED statement will be used.

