9.3.4.1. Primary Efficacy Endpoint Analysis

The MADRS is a 10-item scale whose total score can range from 0 to 60. The primary efficacy variable is change from Baseline in MADRS total score at Week 4, for testing superiority of SP-624 vs. placebo in adults with major depressive disorder. The analysis will be completed using observed data without imputation. Scores will be taken at 4 weeks regardless of subject discontinuation from treatment. Subjects will not be treated with any other antidepressant medication until at least the completion of the Week 5 visit.

The change from Baseline in MADRS total score at Week 4 will be analyzed from the difference in least square mean change using MMRM, with change from Baseline in MADRS total score at each visit as the response variable. The MMRM model will include age, weight, and baseline

MADRS total score as covariates, with factors for treatment, visit (Weeks 1, 2, 3, and 4; as a categorical variable), treatment by visit interaction term, gender, and site as a fixed effect. An unstructured covariance matrix will be used for the within-subject correlation. Kenward-Rogers approximation will be used to calculate the denominator degrees of freedom. The primary efficacy endpoint will be calculated using an estimate statement. Subjects from low enrolling sites may be pooled in order to help with model convergence.

In the event of a model which fails to converge, additional strategies to address convergence may be required such as alternative covariance structures, using a maximum likelihood versus restricted maximum likelihood (REML) estimation, or dropping variables.

The protocol may include approximately 40 sites and sites with less than 10 subjects will be pooled to obtain at least 10 subjects. Sites would be pooled in order of the site number and, if necessary, the last un-pooled site will be pooled with the last set of sites pooled.

Additional variables of interest that may be evaluated as covariates will be identified in the SAP, such as age of onset of depression and number of lifetime episodes.

Additionally, results from the primary outcome will be summarized for the PP population.

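### The SAP's primary MMRM adds a random subject effect to an unstructured covariance: one parameter too many, and an avoidable route into the fallback structures

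*SAP*

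**What the plan says.** SAP section 8.3.5.4 (Primary Efficacy Analysis) lists model terms for treatment, "week and the interaction of week by treatment, and a random effect of subject within treatment", with baseline MADRS as covariate. The same paragraph adds: "An unstructured covariance matrix will be used to model the correlation among repeated measures". For degrees of freedom: "The Kenward-Rogers approximation will be used for the denominator degrees of freedom".

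The fallback rule is: "In the event of a model which fails to converge, the following covariance structures will be considered (in order) until convergence is obtained". The order is heterogeneous Toeplitz, Toeplitz, AR(1), compound symmetry. Then: "If a covariance structure other than Type=UN is used, a sandwich estimator using the EMPIRICAL option on the PROC MIXED statement will be used". The rule changes only the covariance structure. It does not say that the random effect is dropped, and it does not define failure to converge.

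Protocol section 9.3.4.1 uses Weeks 1 to 4 as a categorical visit factor and says: "An unstructured covariance matrix will be used for the within-subject correlation". It names no random subject effect. SAP section 2.2 lists one change from the protocol, the safety population definition. SAP section 8.3.5.5, when naming the variables of the primary analysis for multiple imputation, gives week, treatment, their interaction and baseline score only.

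**The concern.** A random subject intercept and an unstructured residual matrix describe the same thing twice. The intercept adds one constant to every variance and covariance, and the unstructured matrix can already take any such values. The likelihood is therefore flat in one direction.

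Two programmers following this text could handle that differently: one lets the redundant variance go to zero and reports the unstructured fit, while another sees a singular Hessian, calls it non-convergence and starts down the fallback list. The second route changes the covariance structure and the type of standard error behind the only primary test, for a reason unrelated to the data. The SAP also leaves Kenward-Roger in force there alongside sandwich errors, although Kenward-Roger is derived for model-based ones.

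The wording reaches further than the primary test. Section 8.3.5.5 refits the same model to each of 100 imputed data sets, section 8.3.5.6 reuses it for the age and site analyses, and section 8.3.6 uses similar models for the secondary endpoints.

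**Working it through.** **Plan's own figure.** The plan gives no covariance figure to reproduce. Its sample size does reproduce: difference 3, SD 9.2, 80% power, two-sided 0.05 needs 149 per arm by the two-sample t test, and 150 per arm gives 80.4%. It does not depend on this clause.

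**Step 1: count.** I read the clause as one random-intercept variance σ_b². With p = 4 visits (Weeks 1 to 4), an unstructured matrix R has p(p+1)/2 = 4 × 5 / 2 = 10 parameters. The marginal covariance is V = σ_b² J + R, with J all ones, so V_jk = σ_b² + R_jk. Adding c to σ_b² and subtracting c from every R_jk leaves V, and hence the likelihood, unchanged. That makes 11 parameters for 10 quantities. Any σ_b² from 0 up to 1/(1′V⁻¹1) is allowed, where 1 is a vector of ones.

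**Step 2: same count for the fallbacks**, by numerical rank of the map from parameters to the 10 elements of V.

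| Structure | Alone | With random effect | Rank |
|---|---|---|---|
| Unstructured | 10 | 11 | 10 |
| Heterogeneous Toeplitz | 7 | 8 | 8 |
| Toeplitz | 4 | 5 | 4 |
| AR(1) | 2 | 3 | 3 |
| Compound symmetry | 2 | 3 | 2 |

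Toeplitz and compound symmetry have the same redundancy. Heterogeneous Toeplitz, the first fallback, is identified at the unequal visit variances used.

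**Step 3: REML fits on one simulated data set.** Assumptions: 300 subjects, 24.7% missing at Week 4, an assumed covariance with Week 4 SD 9.2.

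- Unstructured only: -2 REML log-likelihood 4883.691; Week 4 difference -3.662, SE 1.196.
- With the random effect, from starting values 0.1, 10 and 20: σ_b² ended at 0.30, 9.84 and 19.55. All three gave 4883.691, -3.662 and 1.196.
- The 11 × 11 Hessian has one eigenvalue near 4e-11; the others run from 0.03 to 1.7. The flat range for σ_b² is 0 to about 29.2.

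The optimizer flagged none of the three fits as successful. It was a general-purpose routine, so this is not evidence about PROC MIXED.

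**Step 4: degrees of freedom.** The variance of the Week 4 contrast depends on the parameters only through V, so its gradient has no component in the flat direction, and any generalized inverse of the information matrix gives the same result. A check on a second simulated data set (300 subjects, 18% missing at Week 4, assumed covariance), with the Satterthwaite-type df for a single contrast, gave SE 1.1389 and df 268.33 for plain unstructured. Adding the random effect gave the same values under two different generalized inverses.

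**Step 5: size if the fallbacks are used.** On the Step 3 data, the four structures without the random effect gave Week 4 differences from -3.560 (compound symmetry) to -3.728 (AR(1)), with sandwich SEs 1.191 to 1.196. Against -3.6625, the largest departures are 3.6625 - 3.5603 = 0.102 and 3.7277 - 3.6625 = 0.065, or 0.102/1.196 = 0.09 SE and 0.065/1.196 = 0.05 SE. Dropout there did not depend on earlier scores.

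A separate simulation assumed about 18% dropout differing by arm, with a true difference of -3.0. It gave -3.05 under unstructured and about -2.88 under AR(1) with the random effect or compound symmetry. That shift is 3.05 - 2.88 = 0.17, or 0.17/1.2 = 0.14 of the SE at the planned size.

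**Step 6: two-visit scales.** HAM-D-17, SDS, QIDS-SR and Q-LES-Q-SF have only Weeks 2 and 4 after baseline. There, adding the random effect is redundant with every listed structure: 4 parameters against 3 for unstructured and heterogeneous Toeplitz, and 3 against 2 for the rest.

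**The case against.** The best defence is that nothing in the primary result changes. Only the split between σ_b² and R is undetermined; V, the Week 4 difference, its model-based SE and the degrees of freedom are all determined. If the software sets the redundant variance to zero, the fit is exactly the unstructured model. A singular-Hessian warning is not plainly a failure to converge, and no one has shown that PROC MIXED would stop. Even then, the first fallback is identified and the shifts in Step 5 are small. The phrase may also be loose wording for the subject block of the repeated measures: the SAP speaks of a single Type=UN structure and omits the random effect from its list of primary-analysis variables.

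Most of this stands, and it rules out three stronger readings that a reader might infer: that the treatment effect is biased, that the primary SE and p-value are arbitrary, or that Kenward-Roger cannot be computed. Steps 3 and 4 contradict all three as long as the fit stays on the unstructured matrix.

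The defence does not remove the defect. The SAP never says that the subject term only defines the block, and it leaves the trigger for the fallbacks undefined. Section 8.3.6 lets the secondary models be reduced for convergence problems, but section 8.3.5.4 gives no such rule for the primary. The pairing of sandwich errors with Kenward-Roger is a separate gap that would exist without the random effect; it is raised here because the same edit closes it.

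**Conclusion.** The point holds as a specification error that should be fixed, not as a demonstrated bias. The over-parameterisation (11 for 10) is algebra and needs no assumption beyond reading the clause as one subject variance. The cost is an avoidable chance that a singular fit is treated as non-convergence and the primary test moves to a restricted covariance with sandwich errors. That chance is unquantified. If it happened, the change in the Week 4 estimate is likely small: about 0.05 to 0.14 SE at the extremes compared here, under assumed covariance and dropout patterns that the documents do not give. The sample size is unaffected.

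**What to change.** In SAP section 8.3.5.4, delete the random subject effect, or state that subject only identifies the repeated-measures block with TYPE=UN. Either edit restores the covariance specification of protocol section 9.3.4.1. It does not address the protocol's other covariates, which are outside this point.

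State that no random subject effect enters any fallback step, or the refits and secondary models that reuse this specification. State that when EMPIRICAL is used, a named method other than Kenward-Roger supplies the degrees of freedom. A sentence defining failure to converge, and saying whether a singular Hessian counts, would be a useful addition.

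The cost is one clause removed and two or three sentences added. No data collection, sample size or estimand changes.
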